9.2 Methods and Timing for Assessing, Recording, and Analyzing Safety Parameters

9.2.1 Adverse Events

Adverse Event (AE): (ICH) E6 defines an AE as any untoward medical occurrence in a patient or clinical investigation subject administered a pharmaceutical product regardless of its causal relationship to the study treatment. An AE can therefore be any unfavorable and unintended sign (including an abnormal laboratory finding), symptom, or disease temporally associated with the use of a medicinal (investigational) product. The occurrence of an AE may come to the attention of study personnel during study visits and interviews of a study recipient presenting for medical care, or upon review by a study monitor.

AEs, including solicited injection site and systemic (subjective and quantitative) reactions, not meeting the protocol-defined criteria for SAEs will be captured on the appropriate DCF and eCRF. Information to be collected for unsolicited non-serious AEs includes event description, date of onset, licensed study clinician's assessment of severity and relationship to study product and alternate etiology (if not related to study product) (assessed only by those with the training and authority to make a diagnosis and listed on the Form FDA 1572 as the site principal investigator or sub-investigator), date of resolution of the event, seriousness, and outcome. AEs occurring during the trial collection and reporting period will be documented appropriately regardless of relationship. AEs will be followed through resolution.

Any medical condition that is present at the time that the subject is screened will be considered as baseline and not reported as an AE. However, if the severity of any pre-existing medical condition increases, it will be recorded as an AE.

AEs must be graded for severity and assessed for relationship to study product (see definitions below). AEs characterized as intermittent require documentation of onset and duration of each episode. The start and stop date of each reported AE will be recorded on the appropriate DCF and eCRF.

FDA defines an AE as any untoward medical occurrence associated with the use of a drug in humans, whether or not considered drug related.

New-Onset Chronic Medical Conditions (NOCMCs): NOCMCs are defined as any new ICD-10 diagnosis that is applied to the subject during the duration of the study, after receipt of the study agent, that is expected to continue for at least 3 months and requires continued health care intervention.

Medically-Attended Adverse Events (MAAEs): For each unsolicited AE experienced, the subject will be asked if he/she had received medical attention, defined as hospitalization, an ER visit, or an otherwise unscheduled visit to or from medical personnel for any reason. AEs characterized by such unscheduled medical care will be designated as MAAEs.

Potentially Immune-Mediated Medical Conditions (PIMMCs): PIMMCs constitute a group of AEs that includes diseases which are clearly autoimmune in etiology and other inflammatory and/or neurologic disorders which may or may not have autoimmune etiologies. PIMMCs currently in effect are presented in [Appendix B: List of PIMMCs](#).

Severity of Event: AEs will be assessed by a licensed study clinician listed on the Form FDA 1572 as the site principal investigator or appropriate sub-investigator using a protocol-defined grading system (see [Sections 9.2.2](#) and [9.2.3](#)). For events not included in the protocol-defined grading system, the following guidelines will be used to quantify severity:

- **Mild (Grade 1)**: Events require minimal or no treatment and do not interfere with the subject's daily activities.
- **Moderate (Grade 2)**: Events result in a low level of inconvenience or concern with therapeutic measures. Moderate events may cause some interference with functioning and daily activities.
- **Severe (Grade 3)**: Events interrupt the subject's daily activities and may require systemic drug therapy or other treatment. Severe events are usually incapacitating.

Relationship to Study Product: The licensed study clinician's assessment of an AE's relationship to study product is part of the documentation process, but it is not a factor in determining what is or is not reported in this trial. If there is any doubt as to whether a clinical observation is an AE, the event should be reported. The relationship to study product must be assessed for AEs using the terms: related or not related. In a clinical trial, the study product must always be suspect. To help assess, the following guidelines are used:

- **Related** – There is a reasonable possibility that the study product caused the AE. Reasonable possibility means that there is evidence to suggest a causal relationship between the study product and the AE.
- **Not Related** – There is not a reasonable possibility that the administration of the study product caused the event.

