3.2.2 Secondary

Safety:

- Occurrence of study vaccine-related unsolicited non-serious AEs following each study vaccination through approximately 21 days after each study vaccination.
- Occurrence of all unsolicited non-SAEs following each study vaccination through approximately 21 days after each study vaccination.
- Occurrence of MAAEs, including NOCMCs and PIMMCs, following the first study vaccination through approximately 12 months after the last study vaccination.

Immunogenicity:

- For HAI and Neut antibodies, percentage of subjects achieving seroconversion against the 2017 H7N9 vaccine strain at approximately 21 days after receipt of 1 dose of AS03-adjuvanted 2017 H7N9 IIV (Group 1 – Day 22; Group 2 – Day 43; Group 3 – N/A).
- For HAI and Neut antibodies, percentage of subjects achieving serum HAI and Neut antibody titers $\geq 1:40$ against the influenza 2017 H7N9 vaccine strain at baseline and approximately 21 days after receipt of 1 dose of AS03-adjuvanted 2017 H7N9 IIV (Group 1 – Day 1 (baseline) and Day 22; Group 2 – Day 22 (baseline) and Day 43; Group 3 – N/A).
- GMTs of serum HAI and Neut antibodies against the influenza 2017 H7N9 vaccine virus at baseline and at approximately 21 days after receipt of 1 dose of AS03-adjuvanted 2017 H7N9 IIV. (Group 1 – Day 1 (baseline) and Day 22; Group 2 – Day 22 (baseline) and Day 43; Group 3 – N/A).

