9.2.2 Reactogenicity

Reactogenicity events are AEs that are common and known to occur following administration of this type of study vaccine. The following Toxicity Grading Scales will be used to grade solicited local (injection site) and systemic (subjective and quantitative) reactions:

Injection Site Reactogenicity Grading

Injection Site Reaction	Mild (Grade 1)	Moderate (Grade 2)	Severe (Grade 3)
Pain – experienced without touching the injection site (spontaneous discomfort)	Subject is aware of pain, but it does not interfere with daily activity, and no pain medication is taken	Subject is aware of pain; there is interference with daily activity or it requires repeated use of a non-narcotic pain reliever for >24 hours	Subject is aware of pain, and it prevents daily activity or requires any use of a narcotic pain reliever
Tenderness – hurts only when injection site is	The area immediately surrounding the injection	The area immediately surrounding the injection	The area immediately surrounding the injection

Injection Site Reaction	Mild (Grade 1)	Moderate (Grade 2)	Severe (Grade 3)
touched or the arm is moved	site hurts only when touched or with arm motion, and it does not interfere with daily activity	site hurts when touched or with arm motion, and it interferes with daily activity	site hurts when touched or with arm motion, and it prevents daily activity
Pruritus (Itching)	Does not interfere with daily activity	Interferes with daily activity	Prevents daily activity
Ecchymosis (Bruising)*	Does not interfere with daily activity	Interferes with daily activity	Prevents daily activity
Erythema (Redness)*	Does not interfere with daily activity	Interferes with daily activity	Prevents daily activity
Induration (Hardness)/Edema (Swelling)*	Does not interfere with daily activity	Interferes with daily activity	Prevents daily activity

* Will also be measured in mm but size will not be used as halting criteria.

Ecchymosis, erythema, and induration (hardness)/edema (swelling) as analyzed by measurement will be graded as follows:

Local (Injection Site) Reactogenicity Measurements

Local (Injection Site) Reaction	Small	Medium	Large
Ecchymosis (Bruising)*	<20 mm	20 mm – 50 mm	>50 mm
Erythema (Redness)*	<20 mm	20 mm – 50 mm	>50 mm
Induration (Hardness)/Edema (Swelling)*	<20 mm	20 mm – 50 mm	>50 mm

* Will not be used as halting criteria.

Subjective Systemic Reactogenicity Grading

Systemic (Subjective)	Mild (Grade 1)	Moderate (Grade 2)	Severe (Grade 3)

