16.2.7 Adverse Events

Listing 10: 16.2.7.1 - Solicited Events – Systemic Symptoms

Subject ID	Treatment Group	Dose Number	Post Dose Day	Assessment ¹	Symptom	Severity	Attributed to Alternate Etiology? ²	Alternate Etiology
				MA				
				Clinic				

¹ MA = Data reported by subject on the Memory Aid and reviewed by clinic staff and reported in Solicited Events eCRF.
 Clinic = Data collected by clinic staff during physical exam or symptom assessment (treatment administration record, in-clinic assessment, etc.)
² Grade 3 events only.

Listing 11: 16.2.7.2 - Solicited Events – Local Symptoms

[Implementation Note: For group 1, dose 1 match the product received to symptoms reported based on the arm the product (IIV4, A/H7N) was received in]

Subject ID	Treatment Group	Dose Number	Product Received ¹	Post Dose Day	Assessment ²	Symptom	Severity
					MA		
					Clinic		

¹ For Group 1, IIV4 and A/H7N9 vaccines are both received at Dose 1 in separate arms.

² MA = Data reported by subject on the Memory Aid and reviewed by clinic staff and reported in Solicited Events eCRF.

Clinic = Data collected by clinic staff during physical exam or symptom assessment (treatment administration record, in-clinic assessment, etc.)

Listing 12: 16.2.7.3 - Unsolicited Adverse Events

Adverse Event	Associated with Dose #	# of Days Post Associated Dose (Duration)	Severity	SAE? MAAE? PIMMC?	Relationship to Study Treatment	In Not Related, Alternative Etiology	Action Taken with Study Treatment	Subject Discontinued Due to AE	Outcome	MedDRA® System Organ Class	MedDRA® Preferred Term
Subject ID: , Treatment Group: , AE Number:											
				SAE: No MAAE: Yes PIMMC: No							
Comments:											
Subject ID: , Treatment Group: , AE Number:											
Comments:											
Note: For additional details about SAEs, see Section 14.3.3											

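### The medical-attention question is asked only for unsolicited AEs, so a non-serious solicited reaction that leads to an ER or unscheduled visit has no specified route into the MAAE endpoint

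*Protocol*

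**What the plan says.** The secondary safety endpoint in Protocol 3.2.2, repeated in SAP 3.2.2, is "Occurrence of MAAEs, including NOCMCs and PIMMCs, following the first study vaccination through approximately 12 months after the last study vaccination". Protocol 9.1 lists MAAEs as a safety parameter separate from both solicited and unsolicited AEs.

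Protocol 9.2.1 defines the term in two steps. The first is the question put to subjects: "For each unsolicited AE experienced, the subject will be asked if he/she had received medical attention". Medical attention there means hospitalization, an ER visit or some other unscheduled contact with medical personnel. The second is the designation: "AEs characterized by such unscheduled medical care will be designated as MAAEs".

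The same section treats reactogenicity as part of the AE universe, with the phrase "AEs, including solicited injection site and systemic (subjective and quantitative) reactions". Protocol 9.2.2 agrees: "Reactogenicity events are AEs that are common and known to occur following administration of this type of study vaccine".

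The SAP adds no MAAE definition of its own. Its unsolicited AE listing (Listing 12) has a column headed "SAE? MAAE? PIMMC". The two solicited listings, Listing 10 ("16.2.7.1 - Solicited Events – Systemic Symptoms") and Listing 11 (local symptoms), have no such column. MAAEs are displayed as a count row in Table 100 and as a listing in Table 125.

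**The concern.** The endpoint counts MAAEs from the first vaccination onward, which includes the 7-day reactogenicity window after each dose. Within that window a visit for a listed symptom, such as fever or injection-site pain, is recorded under solicited AEs, where the plan does not ask about care sought. Visits of this kind are among the medically attended events most plausibly caused by the vaccine.

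Two things are at stake. Events may be missing from the MAAE displays, and sites may classify the same event differently because no rule is given. If the question is not asked when the reaction occurs, nothing in the planned solicited-event outputs would let an analyst reconstruct the answer later.

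**Working it through.** This is a matter of definition, so the check is mainly a comparison of texts.

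**1. Scope of the endpoint.** Protocol 3.2.2 and SAP 3.2.2 use the defined term MAAE. They neither restrict it to unsolicited events nor say that every medically attended AE counts. The meaning therefore rests on Protocol 9.2.1.

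**2. The definition.** The question is limited to unsolicited AEs. The designation sentence says AEs without that limit, but its word for the care in question points back to the preceding sentence. The text does not settle whether a solicited reaction can qualify.

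**3. Fields planned for each event type.** Protocol 9.2.1 gives a detailed item list only for one type: "Information to be collected for unsolicited non-serious AEs includes event description, date of onset", and so on. SAP Listing 10 shows dose, day, source of assessment, symptom, severity and alternate etiology. Listing 11 shows dose, product, day, source, symptom and severity. Neither records medical attention.

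**4. Whether severity grade could stand in.** Protocol 9.2.2 grades solicited reactions by effect on daily activity, by pain-reliever use (pain only) or by temperature, and it also measures some local reactions in mm. No grade depends on care sought, so a visit cannot be recovered from the grade.

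**5. Other routes.**
- Under Protocol 9.2.4 a reaction that leads to hospitalization or meets another serious criterion is an SAE, whether solicited or not.
- Protocol 6.6 says that a new medication should prompt an MAAE evaluation. That covers only visits followed by a new medication, and it relies on the same defined term.
- A diagnosis outside the fixed solicited list is an unsolicited AE, so the question is asked.

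What remains is a listed symptom, within 7 days of a dose, with non-serious unscheduled care.

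**6. Direction.** Protocol 2.3.1 reports higher rates of solicited local and systemic AEs with AS03-adjuvanted antigen than with antigen alone, a licensed IIV3 or placebo. If care-seeking per reaction is similar across groups (an assumption), missed events would fall more on Groups 1 and 2 than on Group 3.

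**7. Size.** The documents give no rate for medically attended solicited reactions. Protocol Table 3 uses P(at least one) = 1 − (1 − p)^N. At p = 1% this gives 26.0%, 45.3% and 70.1% for N = 30, 60 and 120, matching the plan's 26, 45 and 70. Applying the formula to the 120 H7N9 recipients, with p assumed:

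| Assumed p | Expected subjects (120p) | P(at least one occurs) |
|---|---|---|
| 0.5% | 0.6 | 45.2% |
| 1% | 1.2 | 70.1% |
| 2% | 2.4 | 91.1% |

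These are chances that such an event occurs, not that it is missed. The 1% row coincides with Table 3 only because the arithmetic is the same; Table 3 concerns a generic safety event.

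**The case against.** The strongest reply is that there is no conflict. The endpoint uses a defined term, 9.2.1 is its only definition, and wanting a broader one is a preference. It is true that the endpoint does not say it covers any medically attended AE, so a reader who infers a flat contradiction goes further than the text.

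A reader might also infer that such a reaction is never scored, with zero chance of appearing as an MAAE. The documents do not say so. No sentence excludes solicited reactions, the designation sentence says AEs, Protocol 6.6 gives another prompt, and the MAAE row in Table 100 and the title of Table 125 are not limited to unsolicited events. The case report forms and manual of procedures are not available here, so the fields actually collected are unknown.

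Nor is follow-up lost. Protocol 9.2.1 and 9.4 follow AEs to resolution, and 5.2.4 applies this to solicited reactions still ongoing at early withdrawal.

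Finally, it would be too strong to speak of a biased treatment comparison. Protocol 11.6.2 expects few MAAEs and plans listings, and Table 100 gives n and % without an interval or test. The modelled reactogenicity comparison in SAP 9.3.1 uses the solicited events themselves, which are a primary endpoint.

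All of this stands and narrows the point. It does not supply the missing question or field.

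**Conclusion.** The concern holds as an ascertainment gap. The only medical-attention question is tied to unsolicited AEs, and neither document says whether a medically attended solicited reaction is an MAAE. The planned solicited-event outputs record nothing from which the answer could be recovered. The reaction itself is still captured and graded, and serious cases are SAEs.

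The gap affects one secondary, descriptive endpoint. Sample size, power, alpha and follow-up to resolution are untouched. Its size cannot be taken from the documents: 0.6 to 2.4 subjects among 120 follows only from an assumed rate of 0.5% to 2%. The likely direction, an under-count falling more on Groups 1 and 2, rests on the protocol's statement about AS03 reactogenicity plus the assumption of similar care-seeking per reaction. With few MAAEs expected, one or two unrecorded events could change how the displays read. The conclusion also assumes that the forms follow the protocol wording and the SAP shells.

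**What to change.** - In Protocol 9.2.1, extend the medical-attention question to each AE experienced, whether solicited or unsolicited.
- Ask it at the memory-aid reviews that Protocol 7.1 already schedules at about 3 and 7 days after each vaccination.
- Add an MAAE flag to SAP Listings 10 and 11.
- Include flagged solicited reactions in Tables 100 and 125, identified as solicited.
- State that a clinic visit requested by the study team does not by itself make a reaction an MAAE. The visit sections in Protocol 8 allow subjects to be called back after a reported reaction, and without this rule those recalls could inflate the count.

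The cost is one changed protocol sentence plus the recall rule, one yes/no item on the solicited-event form, and a second data source for two SAP tables. Some events will appear in both the solicited and MAAE displays, which a footnote can explain.

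Stating that MAAEs are limited to unsolicited AEs, in the endpoint and in both tables, would remove the ambiguity but would leave the visits unrecorded. It is the weaker option.

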9.2.2 Reactogenicity

Reactogenicity events are AEs that are common and known to occur following administration of this type of study vaccine. The following Toxicity Grading Scales will be used to grade solicited local (injection site) and systemic (subjective and quantitative) reactions:

Injection Site Reactogenicity Grading

Injection Site Reaction	Mild (Grade 1)	Moderate (Grade 2)	Severe (Grade 3)
Pain – experienced without touching the injection site (spontaneous discomfort)	Subject is aware of pain, but it does not interfere with daily activity, and no pain medication is taken	Subject is aware of pain; there is interference with daily activity or it requires repeated use of a non-narcotic pain reliever for >24 hours	Subject is aware of pain, and it prevents daily activity or requires any use of a narcotic pain reliever
Tenderness – hurts only when injection site is	The area immediately surrounding the injection	The area immediately surrounding the injection	The area immediately surrounding the injection

Injection Site Reaction	Mild (Grade 1)	Moderate (Grade 2)	Severe (Grade 3)
touched or the arm is moved	site hurts only when touched or with arm motion, and it does not interfere with daily activity	site hurts when touched or with arm motion, and it interferes with daily activity	site hurts when touched or with arm motion, and it prevents daily activity
Pruritus (Itching)	Does not interfere with daily activity	Interferes with daily activity	Prevents daily activity
Ecchymosis (Bruising)*	Does not interfere with daily activity	Interferes with daily activity	Prevents daily activity
Erythema (Redness)*	Does not interfere with daily activity	Interferes with daily activity	Prevents daily activity
Induration (Hardness)/Edema (Swelling)*	Does not interfere with daily activity	Interferes with daily activity	Prevents daily activity

* Will also be measured in mm but size will not be used as halting criteria.

Ecchymosis, erythema, and induration (hardness)/edema (swelling) as analyzed by measurement will be graded as follows:

Local (Injection Site) Reactogenicity Measurements

Local (Injection Site) Reaction	Small	Medium	Large
Ecchymosis (Bruising)*	<20 mm	20 mm – 50 mm	>50 mm
Erythema (Redness)*	<20 mm	20 mm – 50 mm	>50 mm
Induration (Hardness)/Edema (Swelling)*	<20 mm	20 mm – 50 mm	>50 mm

* Will not be used as halting criteria.

Subjective Systemic Reactogenicity Grading

Systemic (Subjective)	Mild (Grade 1)	Moderate (Grade 2)	Severe (Grade 3)
Feverishness (Chills/Shivering/Sweating)	No interference with daily activity	Some interference with daily activity	Significant interference, prevents daily activity

Systemic (Subjective)	Mild (Grade 1)	Moderate (Grade 2)	Severe (Grade 3)
Fatigue (Tiredness)	No interference with daily activity	Some interference with daily activity	Significant interference, prevents daily activity
Malaise (General Unwell Feeling)	No interference with daily activity	Some interference with daily activity	Significant interference, prevents daily activity
Myalgia (Body Aches/Muscular Pain)*	No interference with daily activity	Some interference with daily activity	Significant interference, prevents daily activity
Arthralgia (Joint Pain)*	No interference with daily activity	Some interference with daily activity	Significant interference, prevents daily activity
Headache	No interference with daily activity	Some interference with daily activity	Significant interference, prevents daily activity
Nausea	No interference with daily activity	Some interference with daily activity	Significant interference, prevents daily activity

* Not at injection site.

Oral temperature[#] will be graded as follows:

Quantitative Systemic Reactogenicity Grading

Systemic (Quantitative)	Mild (Grade 1)	Moderate (Grade 2)	Severe (Grade 3)
Fever* - oral [†]	38.0°C – 38.4°C 100.4°F – 101.1°F	38.5°C – 38.9°C 101.2°F – 102.0°F	>38.9°C >102.0°F

Oral temperature assessed on Day 1 prior to the first study vaccination will be considered as baseline.

* A fever can be considered not related to the study product if an alternative etiology can be documented.

† Subjects must not eat or drink anything hot or cold, or smoke within 10 minutes prior to taking oral temperature.

9.2.3 Additional Adverse Event Severity Grading

Pulse and blood pressure[#] will be graded as follows:

Physiologic Parameter	Mild (Grade 1)	Moderate (Grade 2)	Severe (Grade 3)
Bradycardia - beats per minute	45 – 46	40 – 44	<40

Tachycardia - beats per minute	101 – 130	131 – 155	>155
Hypotension (systolic) mmHg	80 – 84	75 – 79	<75
Hypotension (diastolic) mmHg	50 – 54	45 – 49	<45
Hypertension (systolic) mmHg	151 – 155	156 – 160	>160
Hypertension (diastolic) mmHg	96 – 100	101 – 105	>105

Pulse and blood pressure assessed on Day 1 prior to the first study vaccination will be considered as baseline.

For Individuals ≥ 65 years of age, pulse and blood pressure[#] will be graded as follows:

Physiologic Parameter	Mild (Grade 1)	Moderate (Grade 2)	Severe (Grade 3)
Bradycardia - bpm	45 – 46	40 – 44	<40
Tachycardia – bpm	101 – 130	131 – 155	>155
Hypotension (systolic) mm Hg	80 – 84	75 – 79	<75
Hypotension (diastolic) mm Hg	50 – 54	45 – 49	<45
Hypertension (systolic) mm Hg	161 – 165	166 – 170	>170
Hypertension (diastolic) mm Hg	96 – 100	101 – 105	>105

[#] Pulse and blood pressure assessed on Day 1 prior to the first study vaccination will be considered as baseline.

Clinical safety laboratory results[#] will be graded as follows:

Clinical Safety Laboratory Adverse Event Grading⁷⁵

Hematology	Mild (Grade 1)	Moderate (Grade 2)	Severe (Grade 3)
WBC 10 ³ /µL (Decrease)	2.5 – 3.9	1.5 – 2.4	<1.5
WBC 10 ³ /µL (Increase)	10.6 – 15.0	15.1 – 20.0	>20.0
Hgb g/dL (Decrease) (Female)	10.1 – 11.4	8.5 – 10	<8.5
Hgb g/dL (Decrease) (Male)	11.0 – 12.4	9.5 – 10.9	<9.5
Platelets 10 ³ /µL (Decrease)	125 – 139	100 – 124	<100
Platelets 10 ³ /µL (Increase)	416 – 550	551 – 750	>750

Chemistry	Mild (Grade 1)	Moderate (Grade 2)	Severe (Grade 3)
ALT IU/L (Increase) (Female)	44 – 100	101 – 200	>200
ALT IU/L (Increase) (Male)	61 – 138	139 – 275	>275
Total Bilirubin mg/dL (Increase) – when accompanied by any increase in ALT	1.30 – 1.59	1.60 – 1.80	>1.80
Total Bilirubin mg/dL (Increase) – when ALT is normal	1.30 – 1.89	1.90 – 2.40	>2.40
Creatinine mg/dL (Increase) (Female)	1.1 – 1.7	1.8 – 2.0	>2.0
Creatinine mg/dL (Increase) (Male)	1.4 – 1.7	1.8 – 2.0	>2.0

[#] Clinical laboratory evaluations assessed on Day 1 prior to the first study vaccination will be considered as baseline.

